### 8.2.2 Left Ventricular Thickness

One key outcome for the cardiovascular aim is change in left ventricular (LV) thickness, as measured by echocardiogram at the visit 2 and every other year thereafter. LV thickness will be quantified as the LV mass index in units of g/m2.7. We will also explore use of interventricular and posterior wall thicknesses, but constrain ourselves here to LV mass index. Due to the timing of the echocardiography, we will have approximately 300 children with two measurements of LV thickness during the 1st funding cycle: the analysis described below is restricted to these approximately 300 children.

Let Yi be the 2-year change in LV thickness measured in units of  $g/m^{2.7}$  for child i (= yij - yij-2). We will fit a regression model for the effect of decline in GFR on the change in LV thickness of the form Yi = b0 + b1ti + b2LVi + b3Gi, where ti measures the time between the two echocardiograms, centered at 2 years (= (tij - tij-2) - 2), the variable LVi measures the baseline LV thickness, centered at its mean, and Gi is the decline of GFR in the year preceding the baseline LV measurement scaled to a 5-unit difference (= (GFRij-1 - GFRij)/5). This model will describe the average change in LV thickness as b0 for those with 2 years between echocardiograms, average LV thickness at baseline, and no GFR decline. Individuals with 2-years between echocardiograms and average baseline LV thickness who exhibit a GFR decline of 5 ml/min|1.73m^2 will have an

average change in LV thickness of  $b_0 + b_3$ , such that  $b_3$  quantifies the effect of GFR decline on change in LV thickness.

The above regression will be extended to control for possible confounding by age since diagnosis, blood pressure and body mass index by the addition of +  $b_4A_i + b_5SBP_i + b_6BMI_i$ , where  $A_i$  is the percent of a child's age that the child has lived with CKD centered about 50% (= [100(t – age of diagnosis of CKD) / t ] – 50), SBP\_i is the average of two clinical systolic blood pressure measurements, and BMI\_i is the child's body mass index. Here  $b_4$  is quantifies the shift of the regression line for a one percent increase in age since CKD diagnosis. For example, in children 12 years of age, those who have had CKD since age 9 versus those who have had CKD since age 6 will differ in Y12 by  $b_4[100x(6/12 - 3/12)]= 25b_4$ . The parameters  $b_5$  and  $b_6$  quantify the effects of a 1-unit increase in systolic blood pressure and body mass index on the shift of the regression line, respectively. In this extended model,  $b_3$  estimates the effect of a decline of 5 ml/min[1.73m^2 of GFR, adjusting for age at diagnosis, systolic blood pressure, and body mass index.

To explore potential effect modification, the above extended regression model will be stratified by the use of ACE inhibitors and/or quintiles of sodium intake, as measured with a food frequency questionnaire, to assess whether the effect of GFR decline on change in LV thickness differs in the presence of this therapy or salt intake.

Of course, more detailed analysis plans and further delineated analytic models will be possible as data accumulates and hypotheses develop. For instance, the Cardiovascular Subcommittee has expressed interest in the analysis of repeated measurements of clinical blood pressures as well as episodes of nocturnal 'dipping' blood pressure available from ambulatory blood pressure monitoring.

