#### 2.1 Progression of Chronic Kidney Disease

To slow the progression of CKD, and treat the complications of CKD during the formative years of life, an in-depth understanding of the risk factors for progression of pediatric CKD is necessary. Information from the North American Pediatric Renal Transplant Cooperative Study [NAPRTCS 2002] Chronic Renal Insufficiency (CRI) registry, with data on over 5000 children with CKD, suggests several risk factors for renal progression in children [NAPRTCS 2002]. Important risk factors identified by this registry include age (preteen and teenage children progress to ESRD more rapidly than younger children), underlying disease (focal segmental glomerulosclerosis vs. other disorders), and low GFR at entry into the registry. Hypertension, proteinuria, poor nutrition, anemia, hypocalcemia, hyperphosphatemia and hyperparathyroidism are also associated with rapid progression to ESRD.

In adults, race [Brancati 1992, Feldman 1992, Klag 1997, Whittle 1993], family history [Freedman 1993], diet, physical activity, smoking, socioeconomic status, and medical management are associated with progression of CKD, while proteinuria [Iseki 1997, Klahr 1988, Levey 1991, Lewis 1993, Maschio 1996, Ruggenenti 1999], hyperlipidemia, and inflammation [Kasiske 1998, Ruggenenti 2000, Sarnak 2000] are intermediate factors affecting progression. Therefore, risks due to host factors (e.g., genetic susceptibility, sex, race, serum albumin <4 g/dl, phosphate >5.5, proteinuria, hypertension, anemia, and others), exposures external to the host, and medical management will be systematically studied in this prospective cohort of children with CKD. Not only will this study examine traditional risk factors for kidney disease progression. Prospective, standardized data collection and precise measurements of GFR will allow more precise definition of risk factors and will allow us to differentiate between causal and non-causal associations. Non-causal associated factors can be markers for other causal factors (confounding) or markers of the disease itself (reverse causality).

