	Tanner Stage		•		•	•	•	•	٠	•
	Physical Activity Monitoring m			•	•	•	•	•	•	•
	Intact Parathyroid Hormone (iPTH)			•		•			•	•
	High Sensitivity CRP (hsCRP)			•		•			•	•
	Vitamin D			•		•			•	•
	Fibroblast Growth Factor-23 (FGF-23)			•		•			•	•
	Grip Strength n					•			٠	•

Table 5.4.1a Measurements with Time-on-Study as Time Scale Science and Analysis

a Johexol GFR: Iohexol GFR was measured on all Cohort 1 and 2 participants. As of June 2016 amendment, iGFR is measured on a subset of Cohort 1 and 2. In Cohort 3, iGFR will be optional.

a lobexol GFR: lobexol GFR was measured on all COROT 1 and 2 participants. As or june 2010 amenament, fUTK is measured on a subset of CoROT 3, Kerk with be optional.
 b Cohorts 2 & 3: For Cohorts 2 & 3, these tests will be measured at baseline and annual visits. For Cohort 1, the measurements of these tests were initiated at follow-up.
 c Pregnancy Tests: Pregnancy tests will be performed on females of child bearing potential. Childbearing potential occurs when the female has reached menarche.
 d Local Urine Creatinine and Urine Protein: Clinical sites requiring immediate results will perform urine creatinine and urine protein tests at their local laboratory in addition to the tests sent to CBL.
 e ECHO and Carotid IMT: Performed at V2 and every four (4) years thereafter.
 e Condit MT: At selected sites, sub-set of Cohorts 1 and 2 will have carotid IMT performed (N=100). In Cohort 3, the participants who are 5 years old and older will have vascular test performed.
 e Vaccoular Tests: At selected sites, sub-set of Cohorts 1 and 2 will have carotid IMT performed. In Cohort 3, the participants who are 5 years old and older will have vascular test performed.

\* Vascular Tests: At selected sites, sub-set of Cohorts 1 and 2 will have vascular tests performed. In Cohort 3, the participants who are 5 years old and older will have vascular tests performed.
h Home Blood Pressure Monitor: At selected sites, sub-set of the entire cohort will have home blood pressure monitoring.
Cardiac MRI: Sub-set of the entire cohort with a high probability of reaching ESRD will have cardiac MRI performed.

 JNH Toolbox Tests: At selected sites, sub-set of Cohort participants who are 3 years old and older will complete NIH toolbox texts.

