The cardiovascular component will be implemented after the second year and every four (4) years thereafter. The cardiovascular outcomes will be measured while the participants wait for their blood to be drawn for GFR measuring. The same temporality of GFR levels and changes preceding the cardiovascular data (i.e., ECHO) will be provided by our proposed design. The only limitation for the study is that, for Cohort 2, half of the cohort will have only one assessment of cardiovascular risk factors by 2018.

The core markers of neurocognitive function and growth will be measured in the odd years from the third year on. A salient feature of the proposed contact pattern is that the assessment of neurocognitive function will not be perturbed by the requirements of the GFR protocol. The pattern outlined in the table will also be conducive to assessing the impact of the changes in GFR on the changes in neurocognitive function. Specifically, the changes in GFR between year 1 (0 to 12 months) and year 2 could be predictive of the changes in neurocognitive function between year 1 (with a desired lag of six months) and year 3. In addition, the two years in between the assessment of neurocognitive function will minimize practice learning and thus allow a more direct assessment of the impact of kidney disease on neurocognitive development. Finally, the growth component of the study will be conducted at the same time as the neurocognitive component.

In summary, three features of the proposed contact pattern merit emphasis: (i) the GFR measurement in the first two years will provide a measure of GFR change early in the study and it will serve as a good baseline measurement for the long-term change of

GFR; (ii) the availability of concurrent data on GFR and serum creatinine will provide data to develop an internally valid formula which will, in turn, provide the means to complete GFR data by estimating GFR in the odd years; and (iii) both level and changes in GFR will temporally proceed the measurement of the markers of neurocognitive function, cardiovascular risk factors and growth failure.

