## 6.4.1.1 Clinical Measurement of Blood Pressure

Hypertension (HTN) is common in children with CKD [Drukker 1991, Feld 1996, Foreman 1988, Rosenblum 1992, Solhaug 1992] but neither the relative degree of HTN nor the effect of antihypertensive medications on progressive kidney damage has been well studied. A recent report from the NAPRTCS [Mitsnefes 2003a] demonstrated that nearly half of the children enrolled in the CRI registry had HTN based upon an office BP reading obtained at time of enrollment. In that study, hypertensive children with CKD developed ESRD or decrease in GFR > 10 ml/min|1.73m^2 significantly more often after two years of follow-up than normotensive children with CKD, suggesting that HTN is indeed an important factor affecting the rate of progression of CKD in children.

Blood pressure will be measured in a standard fashion by trained, certified observers using an aneroid sphygmomanometer. Appropriately sized cuffs will be used as per the recommendations of the Working Group on High Blood Pressure in Children and Adolescents [HBP Working Group 2004]. Three BPs will be taken at 30 second intervals in the subject's right arm (unless there is a medical reason not to use it) at every study visit. While the use of auscultatory hand held units is sensitive to observer bias, several considerations were made in adopting this general approach. First, the use of a random zero device or mercury sphygmomanometer was removed from consideration due to the American Hospital Association and the Environmental Protection Agency proposals to eliminate mercury from hospitals. Secondly, electronic measurements were not selected, because these devices use an oscillometric technique. Notably, while oscillometric techniques reduce observer bias, accuracy of measurement is compromised, particularly for diastolic blood pressure, because measurements are based on proprietary algorithms of the various device manufacturers. In contrast,
aneroid devices use the auscultatory technique upon which childhood BP standards are based and that is recommended by consensus organizations [HBP Working Group 2004]. Training, certification and blood pressure monitor calibration will be scrupulously maintained.

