### 6.4.1.3 Echocardiography

Echocardiographs will performed by be standard M-mode and Doppler echocardiography. The core outcome measurements will include determination of cardiac structure, systolic and diastolic LV function, and vascular (aortic) compliance. Using cardiac and vessel parameters as dependent variables, the contribution of demographic factors, and clinical and laboratory parameters will be assessed. The decision to use M-Mode for LVM calculation is based on recommendations provided in the 4th Report on High Blood Pressure in Children and Adolescents, prepared by NHLBI's National High Blood Pressure Education Program (NHBPEP). Results from the NHBPEP (which will be published in Pediatrics, August 2004) also emphasize the use of this method as a standard procedure to calculate LVM for pediatric centers. The use of a single and relatively simple method for LVM calculation will provide the standardization among multiple participating centers.

The echocardiogram and Doppler studies will be performed in all children at Visit 2 and every four (4) years thereafter. ECHOs will be performed at individual participating sites and recorded on videotapes, but reading and data analyses of ECHO data will be performed by the Cardiovascular Core Imaging Laboratory, Cincinnati Children's Hospital Medical Center (CCHMC). Videotapes/CDs will be sent to the CCHMC with the assigned study ID number as an identifier. The reading center will not have a list of the names of participants that link to the ECHOs and ECHO reports - these will be held by the local clinical centers. Back-up tapes will be stored at the clinical sites. We anticipate that we will be able to achieve standardization and uniformity of ECHOs across sites through training, certification and pre-specified guality control monitoring. CCHMC has experience in coordinating multicenter studies including coordination of ECHOs for the industry-sponsored ramipril study, "The Effect of Ramipril on Ambulatory Blood Pressure and Left Ventricular Mass Index in Children and Adolescents with Hypertension". ECHOs will be performed by certified technicians, and standardized training and certification of designated ECHO technicians at each clinical center will be required.

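### The worked LV-mass model in Section 8.2.2 is an outdated first-cycle example: it assumes a two-year echocardiogram interval that the current schedule contradicts, does not annualise GFR decline, and has no age or sex term

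*Protocol*

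**What the plan says.** **Echocardiogram interval.** Section 8.2.2 describes LV thickness, quantified as LV mass index, "as measured by echocardiogram at the visit 2 and every other year thereafter". The outcome for child i is defined to "be the 2-year change in LV thickness measured in units of" g/m^2.7, that is, y at visit j minus y at visit j-2. The covariate t_i is the time between the two echocardiograms minus 2 years. The analysis is limited to about 300 children with two measurements in the first funding cycle.

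Three other places give a different interval:
- Section 6.4.1.3: "The echocardiogram and Doppler studies will be performed in all children at Visit 2 and every four (4) years thereafter".
- Section 5.4.1, contact pattern: "The cardiovascular component will be implemented after the second year and every four (4) years thereafter".
- Table 5.4.1a, footnote on echocardiography and carotid IMT: "Performed at V2 and every four (4) years thereafter".

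Two further statements bear on this. Section 6.4 describes repeating the measures two years later in the subcohort enrolled in the first 12 months. Section 5.4.1 also says, in general terms, that core cardiovascular markers are measured every two years.

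**GFR decline.** G_i is described as the GFR decline in the year before the baseline LV measurement and is computed as the difference between consecutive GFR values divided by 5. Section 5.4 sets V2 at one year (plus or minus one month) after V1a, but allows up to two years when scheduling is difficult.

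**Adjustment.** The extended model adds A_i (percent of the child's age lived with CKD, minus 50), SBP_i, which "is the average of two clinical systolic blood pressure measurements", and BMI. The last two have coefficients per one raw unit. There is no term for chronological age or sex.

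**The concern.** This is the protocol's only worked model for the cardiovascular aim. Section 6.4.3 makes within-person change in cardiovascular markers, including echocardiographic measures, a primary outcome of that aim. If the interval in the model is not the interval at which children are measured, an analyst following 8.2.2 either has no eligible pairs or fits the equation to pairs for which its intercept no longer means what the text says.

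The exposure and covariates add to the difficulty. A GFR loss that is not divided by elapsed time treats a slow and a fast decline alike. Age is also a plausible confounder on the protocol's own account: Section 2.1 reports that "preteen and teenage children progress to ESRD more rapidly than younger children", which ties age to the exposure, and LV mass, blood pressure and BMI all change as children grow. The protocol standardises such quantities elsewhere: SBP z-scores in 6.2.1.3.3, BMI percentiles in 6.5.1.1, and sex-specific LV mass index limits in 6.4.1.3.1.

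**Working it through.** **1. The figure of about 300.** The protocol does not derive it. Appendix D plans about 30 recruits per month, so the first 12 months give 30 x 12 = 360. Section 6.4.1.3 expects 510 of about 600 children to remain, a fraction of 0.85. Then 360 x 0.85 = 306, close to 300. The retention fraction is my assumption: 510/586 gives 313 and 510/540 gives 340. The figure is thus consistent with the early subcohort of Section 6.4, who were to be re-measured at two years. The model fits the design for which it was written.

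**2. Echocardiogram pairs at regular visits, V2 to V15.**

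| Schedule | Echo visits | Two-year pairs |
|---|---|---|
| Section 8.2.2 | V2, V4, V6, V8, V10, V12, V14 | 6 consecutive |
| 6.4.1.3, 5.4.1, Table 5.4.1a footnote | V2, V6, V10, V14 | 0 (shortest nominal gap 4 years) |

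**3. Can the visit windows produce a two-year gap?** V2 falls between 1 - 1/12 and 2 years after V1a, and V6 between 5 - 1/12 and 6 years.
- Shortest V2-V6 gap: (5 - 1/12) - 2 = 2.92 years.
- Longest: 6 - (1 - 1/12) = 5.08 years.

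The further one-month allowance in Section 5.4 for a rescheduled echocardiogram moves each echo by at most a month, so the gap still does not reach 2 years.

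**4. Effect on the coefficients.** For V2-V6 pairs t_i is nominally 4 - 2 = +2, and between about +0.9 and +3.1 at the limits. Section 8.2.2 interprets b0 and b0 + b3 at t_i = 0, which lies outside that range, so both become extrapolations. b3 can still be estimated, but from such pairs it describes a difference in change over roughly four years, not two.

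**5. G_i.** Take a loss of 5 ml/min|1.73m², so G = 1.
- Over 12 months the rate is 5 per year.
- Over 24 months it is 5/2 = 2.5 per year, with the same G: a factor of two.
- Inside the target window (11 to 13 months) the rate runs from 5 x 12/13 = 4.6 to 5 x 12/11 = 5.5 per year, so the distortion is small.

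**6. A_i.** The example in 8.2.2 reproduces. At age 12, diagnosis at 6 gives 100 x 6/12 - 50 = 0 and diagnosis at 9 gives 100 x 3/12 - 50 = -25, a difference of 25. For a child diagnosed at birth, A_i = 100(t - 0)/t - 50 = +50 at every age t, so it says nothing about chronological age in that group. The group may be large, since Section 2 says most children with CKD have congenital urologic disease or inherited disorders. Nor does A_i measure age at diagnosis, which 8.2.2 says the model adjusts for: age 12 diagnosed at 6 and age 8 diagnosed at 4 both give 0.

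**The case against.** The best defence is that 8.2.2 never claims to cover current data. It is confined to first-cycle children, Section 6.4 says where their two-year pairs come from, and t_i allows for unequal intervals. Section 8.2 is headed as examples, 8.2.2 expects fuller plans later, and 8.1.1 already describes mixed models for unbalanced data and applies them to cardiovascular markers. The IQ example in 8.2.1 provides for annualising GFR change. Much of this stands, and it rules out several stronger readings:

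- A reader might infer that the two-year outcome does not exist at all. The documents do not support that. The early-subcohort repeat would supply it, and the post-transplant schedule places echocardiograms at even visits (months 12 and 36), though in a different population. Post-dialysis visits also include cardiovascular measurements.
- A reader might infer that the plan discards most of its echocardiograms. The limit to about 300 describes what the first cycle would yield. Setting it against all three cohorts is inapt, since Cohort 3 recruitment began only in late September 2016.
- A reader might try to attach an inflation factor to b3 from mixing two- and four-year pairs, or a bias in g/m^2.7 from age. No passage proposes such mixing, and the protocol gives neither the relation of LV mass change to age nor that of G to age. Indexing to height^2.7, baseline LV mass index, and raw SBP and BMI each absorb part of any age effect.
- Two readings averaged, against "Three BPs will be taken at 30 second intervals" in 6.4.1.1, is a minor mismatch. That section does not say that all three are averaged.

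The defence does not remove the conflict in the interval. The sentence in 8.2.2 describes how echocardiograms are taken and disagrees with three other places in the same document. Nor does 8.2.2 carry over the annualising provision of 8.2.1 or add age or sex.

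**Conclusion.** The point holds as one of consistency and specification. Section 8.2.2 is a first-cycle example left unrevised in a three-cohort protocol. Its interval contradicts 6.4.1.3, 5.4.1 and the Table 5.4.1a footnote, and as written it cannot be applied to regular-visit pairs collected every four years: none of those pairs is two years apart, against six on its own schedule. Its proposed stratification by sodium intake points the same way, because the food frequency questionnaire was discontinued in June 2014 (6.5.1.7).

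Two specification faults accompany this. G_i can misstate the rate of GFR decline by up to a factor of two, but only for children whose V2 falls at the outer limit; the protocol does not say how many those are. The adjusted model leaves residual confounding by age, and possibly sex, whose size and direction cannot be derived from the document.

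The counts assume that visits follow Section 5.4 and that echocardiograms are done at or within a month of the visit. Because the section is illustrative and 8.1.1 contains a suitable method, this should be corrected but does not undermine the cardiovascular aim.

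**What to change.** 1. Reconcile the echocardiogram interval across 8.2.2, 6.4, 6.4.1.3, 5.4.1 (including its general two-year statement on cardiovascular markers) and Table 5.4.1a. If the interval changed over time or differs by subcohort, say when and for whom.
2. Replace the change-score example with the mixed model of 8.1.1, fitted to LV mass index at all available echocardiograms in all cohorts. Use actual years since V2, G, and G x time. The G x time coefficient is then the difference in yearly change in LV mass index, whichever interval applies. State whether echocardiograms after renal replacement therapy are included.
3. Define G as (GFR at V1a - GFR at V2) / (5 x years between them). Iohexol GFR is optional in Cohort 3, so say that estimated GFR is used where it is missing, as 8.2.1 already allows.
4. Add age and sex at V2, enter SBP and BMI as age- and sex-standardised scores, state how many blood pressure readings are averaged, and describe A_i as the share of life lived with CKD rather than as age at diagnosis.

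The cost is redrafting one section, aligning a few sentences elsewhere, and slightly more analysis work. The variables needed are already collected.

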The above regression will be extended to control for possible confounding by age since diagnosis and socioeconomic status by the addition of  $b_4A_{ij}$  and  $b_5SES_{ij}$ , where  $A_{ij}$  is the percent of a child's age that the child has lived with CKD centered about 50% (= [100(t - age of diagnosis of CKD) / t ] - 50) and SESij is the socioeconomic status measured by family income and/or parental educational achievement (For more detail regarding the specification of Age please see section 8.2.1). Here  $b_4$  is quantifies the shift of the regression line for a one percent increase in age since CKD diagnosis. The parameter  $b_5$  quantifies the effect of a 1-unit increase socioeconomic status on the shift of the regression line. In this extended model, the slope  $b_1 + b_3$  estimates the effect of a decline of 5 ml/min|1.73m^2 of GFR, independent of age at diagnosis and socioeconomic status. To explore potential effect modification, the above extended model will be stratified by the presence of psychiatric diagnoses (e.g. ADHD).

In addition to general cognitive functioning as measured by IQ, the Neurocognitive Subcommittee is interested in exploring overall achievement, adaptive and social behavior, and measures of attention.

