The above regression will be extended to control for possible confounding by age since diagnosis and caloric intake by the addition of  $b_4A_{ij}$  and  $b_5C_{ij}$ , where  $A_{ij}$  is the percent of a child's age that the child has lived with CKD centered about 50% (= [100(t – age of diagnosis of CKD) / t ] – 50) and Cij is the caloric and/or protein intake measured by Food Frequency Questionnaire. Here  $b_4$  quantifies the shift of the regression line for a one percent increase in age since CKD diagnosis. The parameter  $b_5$  quantifies the effect of a 1-unit increase in caloric and/or protein intake on the shift of the regression line. In this extended model, the slope  $b_1 + b_3$  estimates the effect of a decline of 5 ml/min|1.73m^2 of GFR, independent of age at diagnosis and caloric intake.

To explore potential effect modification, the above extended model will be stratified by the use of growth hormone and/or steroids to assess whether the effect of GFR decline differs in the presence of these therapies.

In addition to linear growth, we will explore changes in body mass and specific biomarkers, such as iPTH over the course of follow up.

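### Sections 8.2.1 to 8.2.3 explore effect modification only by fitting the model within strata, so the difference that 8.2.2 and 8.2.3 set out to assess is neither estimated nor tested

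*Protocol*

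**What the plan says.** Section 8.2.2 models the two-year change in LV mass index on the time between echocardiograms (b1), baseline LV thickness (b2) and GFR decline in the preceding year, G (b3). On sample size it says that "the analysis described below is restricted to these approximately 300 children", meaning children expected to have two measurements during the first funding cycle. The model then grows by three main effects: "The above regression will be extended to control for possible confounding by age since diagnosis, blood pressure and body mass index". With the intercept that is seven coefficients, b0 to b6.

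Effect modification comes next. The passage opens "To explore potential effect modification, the above extended regression model", says this model "will be stratified by the use of ACE inhibitors and/or quintiles of sodium intake", and gives the purpose as "to assess whether the effect of GFR decline on change in LV thickness differs in the presence of this therapy or salt intake".

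The other two examples follow the same pattern. In 8.2.1 (IQ) the extended model "will be stratified by the presence of psychiatric diagnoses", as an exploration of effect modification. In 8.2.3 (height) it is stratified by growth hormone and/or steroid use "to assess whether the effect of GFR decline differs in the presence of these therapies".

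The only product term anywhere in 8.2 is G × time, in the IQ and height models. It does not involve any of these modifiers.

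**The concern.** Effect modification is a statement about a difference between coefficients. Fitting the model separately in each stratum gives a b3 and a standard error per stratum, but no estimate of how far the b3 values differ and no measure of uncertainty for that difference. Sections 8.2.2 and 8.2.3 name the difference as the question and then give a method that stops one step short of it.

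With small strata, the estimates and their significance will vary by chance even when the true effect is the same everywhere. If nothing in the plan compares them formally, that variation can be mistaken for evidence that a therapy or salt intake changes the effect of GFR decline. Cutting sodium intake into fifths makes each fit smaller still and ignores the ordering of intake unless a trend is fitted.

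**Working it through.** **No figure to reproduce.** The protocol states no power, effect size or residual SD for the LV model or for effect modification. The 300 is a count.

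**Inputs from section 8.2.2:** about 300 children; seven coefficients per fit; ACE inhibitor use (two levels) and/or sodium quintiles (five levels).

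**Assumptions for illustration, not in the protocol:** two-sided 5% tests; whole-cohort power for b3 of 80% (range 50% to 97.5%); equal residual variance and equal spread of G across strata; ACE inhibitor use split 50/50.

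**Stratum sizes**
- Quintile: 300/5 = 60 children, 60 − 7 = 53 residual degrees of freedom.
- Quintile crossed with ACE inhibitor use, if that is done: 300/10 = 30 children, 23 residual degrees of freedom. At a 30/70 split the cells would be 18 and 42.

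**Precision relative to the whole cohort**
- SE(b3) in a stratum of n is √(300/n) times the whole-cohort SE: √5 = 2.24 for a quintile, √10 = 3.16 for a crossed cell of 30.
- The SE of a difference between two of k equal strata is √(2k) times the whole-cohort SE: √4 = 2 for two ACE strata, √10 = 3.16 for two quintiles.

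**Disagreement on significance when the true effect is the same in every stratum**

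Whole-cohort power of 80% puts b3 at 1.96 + 0.84 = 2.80 standard errors.
- Two equal ACE strata: 2.80/√2 = 1.98, so power p is about 0.51 per stratum. Chance that exactly one is significant: 2p(1 − p) = 50%.
- Five quintiles: 2.80/√5 = 1.25, so p = 0.24 per quintile. Chance that they are not all alike: 1 − p⁵ − (1 − p)⁵ = 75%.

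| Whole-cohort power | Power per quintile | Five quintiles disagree | Two ACE strata disagree |
|---|---|---|---|
| 50% | 14% | 53% | 41% |
| 80% | 24% | 75% | 50% |
| 90% | 31% | 84% | 47% |
| 97.5% | 42% | 92% | 33% |

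An interaction test at the 5% level would give a false positive 5% of the time in every row.

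**What a formal test could detect at 80% whole-cohort power**
- G × ACE, 50/50 split, interaction equal to the overall effect: 2.80/2 = 1.40 standard errors, power 29%. Interaction twice the overall effect: 80%.
- Sodium, effect rising linearly from zero to twice the overall effect across quintiles: 51% for a one-degree-of-freedom trend interaction, 31% for a four-degree-of-freedom heterogeneity test.

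At 90% whole-cohort power these four figures become 37%, 90%, 63% and 42%.

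**The case against.** The strongest reply is that the protocol does not say how the strata will be compared, so it has not chosen a wrong comparison. A reader might infer that modification will be declared when one stratum is significant and another is not. The documents do not support that: none of the three sections mentions p-values or any decision rule. A z test or heterogeneity test could also be computed afterwards from the stratum-specific estimates. This reply stands, and it makes the disagreement rates above an illustration of what unaided reading of strata can do. They are not the error rate of a stated procedure.

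Second, section 8.2 is headed as examples, the wording is exploratory, and 8.2.2 expects more detailed plans as data accumulate. Individual projects need a concept sheet with its own statistical methods and power statement (Appendix B) and Steering Committee review (section 3.9.2.1). This also stands and limits the weight of the point.

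Third, several stronger readings go too far:
- Only 8.2.2 and 8.2.3 state the aim of assessing whether the effect differs. Section 8.2.1 says no more than that it explores effect modification.
- Cells of 30 follow only if the two LV modifiers are crossed, which is one reading of and/or, and only at an assumed even split.
- The count of about 300 belongs to the first funding cycle and to the LV model. It says nothing about the IQ and height analyses.

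Fourth, quintiles allow any shape of modification, whereas a single linear sodium term does not, so that choice is partly preference. A non-significant interaction would often be uninformative as well, given the power figures above.

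None of this supplies the missing comparison. The protocol is not silent on method: it writes the models out term by term, selects stratification and, in two sections, ties it to a question about a difference.

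**Conclusion.** The point holds in a limited form. Sections 8.2.1 to 8.2.3 give stratified fits as the only means of exploring effect modification, and in 8.2.2 and 8.2.3 that method does not produce the quantity the stated aim asks for.

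The firm size figures are about 60 children per quintile fit in the first-cycle LV example and a standard error for b3 of about 2.2 times the whole-cohort value, given equal residual variance and spread of G. The disagreement rates of about 50% (two ACE strata) and 75% (five quintiles) rest on assumed power and on a way of reading the strata that the protocol does not state. Over whole-cohort power of 50% to 97.5% they run from 33% to 50% and from 53% to 92%, so the conclusion does not hang on one assumption. Because the analyses are exploratory examples, this is an improvement worth making rather than a flaw that threatens the study.

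**What to change.** Keep the stratum-specific estimates as description and assess modification in one model per modifier:
- **LV (8.2.2):** add the modifier main effect and G × modifier.
- **IQ and height (8.2.1, 8.2.3):** add the modifier, G × modifier, time × modifier and G × time × modifier.
- **Sodium:** enter intake as a continuous or trend-score term, and show quintile estimates to check the shape.

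Report each interaction estimate with its confidence interval and label it exploratory.

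The cost is two added terms for LV and four for IQ or height per binary modifier, with no new data. The single model assumes that confounder coefficients are common to all strata, which separate fits do not. Power will be limited, and the confidence interval makes that visible.
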